22. **Study Treatment:** Axitinib will be given orally twice daily PO on a continuous schedule. MK-3475 will be given as a 30-minute intravenous infusion every 3 weeks. (one Cycle = 3 weeks) (see [Section 5](#)). Patients with disease progression who are continuing to derive clinical benefits from the study treatment will be eligible to continue with study drugs provided that the treating physician has determined that the benefit/risk for doing so is favorable.

23. **Pharmacokinetics:** Samples will be collected at the time points indicated in the [Schedule for Pharmacokinetic Samples Collection](#) Table. Pharmacokinetic samples for MK-3475 will be collected from all patients in the study. Pharmacokinetic samples for axitinib will be collected from all patients in the Dose Finding Phase and at least 8 patients in the Dose Expansion Phase. Details are outlined in [Section 7.2](#).

24. **Serum Biomarkers:** Blood biospecimens (10 mL) will be obtained to measure DNA, RNA or protein markers known or suspected to be of relevance to the mechanism of action, the development of resistance or the identification of those patients who might benefit from treatment with axitinib in combination with MK-3475. Blood biospecimens will be collected at screening, Cycle 2 Day 1 predose, and End of Treatment/Withdrawal whichever comes first. See [Section 7.3.2](#).

25. **Whole Blood Biomarkers:** Blood biospecimen (10 mL) will be obtained to measure DNA, RNA or protein markers known or suspected to be of relevance to the mechanism of action, the development of resistance or the identification of those patients who might benefit from treatment with axitinib in combination with MK-3475. Blood samples will be collected at screening, Cycle 2 Day 1 predose, and End of Treatment/Withdrawal whichever comes first. See [Section 7.3.2](#).

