Discontinuation from MK-3475 may be considered at the investigator's discretion for patients who have attained a confirmed CR, have received at least 24 weeks of treatment with MK-3475, and have received at least two MK-3475 infusions beyond the date the CR was initially declared. Axitinib may be continued in those patients. Patients who then experience radiologic disease progression will be eligible for re-treatment with MK-3475 at the discretion of the investigator if no other cancer treatment was administered other than axitinib since the last dose of MK-3475, the patient still meets the safety parameters listed in the Inclusion/Exclusion criteria, and the trial is still open. Patients will resume MK-3475 therapy at the same dose and schedule in place at the time of discontinuation. MK-3475 treatment will be administered for up to one additional year.

Patients with unacceptable toxicity attributed to one of the two drugs may be eligible for continued treatment with the other drug (after discussion between the Investigator and the Sponsor).

**Tumor assessment:** Anti-tumor activity will be assessed by radiological tumor assessments conducted at baseline, then at 12 weeks and every 6 weeks thereafter, using RECIST version 1.1. In addition, radiological tumor assessments will also be conducted whenever disease progression is suspected (eg, symptomatic deterioration), and at the time of End of Treatment/Withdrawal (if not done in the previous 6 weeks). In determining whether or not the tumor burden has increased or decreased, Investigators should consider all target lesions as well as non-target lesions according to RECIST v 1.1 (see Study Reference Manual).

If radiologic imaging shows PD, tumor assessment should be repeated  $\geq 4$  weeks later in order to confirm PD. Assigned study treatment may be continued at the investigator's discretion while awaiting radiologic confirmation of progression. If repeat imaging does not confirm PD, study treatment may be continued/resumed. Patients that are deemed clinically unstable are not required to have repeat imaging for confirmation of PD and can discontinue treatment immediately.

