If the repeat imaging confirms PD ([Section 5.2.4.1](#)) patients may be discontinued from treatment. However, according to the investigator's clinical judgment and after discussion between the investigator and the Sponsor, if a patient with evidence of disease progression is still experiencing clinical benefit, he/she will be eligible for continued treatment with single agent axitinib, MK-3475 or axitinib combined with MK-3475 as long as the following criteria are met:

- Absence of clinical signs and symptoms of disease progression.
- No decline in performance status.
- Absence of rapid progression of disease by radiographic imaging.
- Absence of progressive tumor at critical anatomical sites (eg, cord compression) requiring urgent alternative medical intervention.

Brain CT or MRI scans are required at baseline and when there is a suspected brain metastasis. Bone scans: Bone scan (bone scintigraphy) or F-FDG-PET/CT is required at baseline then every 12 weeks only if bone metastases are present at baseline. Otherwise bone imaging is required only if new bone metastases are suspected. Bone imaging is also required at the time of confirmation of response for patients who have bone metastases.

Retrospective central review of all imaging time points may be performed for this study, therefore all imaging source data should be retained at the site and be available for future inspection or further analysis. Additional information is included in the Study Reference Manual.

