### **7.3. Translational and Pharmacodynamic Assessments**

A key objective of the biomarker analyses that will be performed in this study is to investigate candidate biomarkers that may have predictive value in identifying those patients who may benefit from treatment with MK-3475 when used in combination with a VEGF inhibitor. In addition, analyses of sequentially obtained tissue and blood biomarkers will provide an opportunity to investigate pharmacodynamic effects. Samples collected at the End of Treatment visit will also help understand potential mechanisms of resistance to the drug combination.

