## Appendix 6. Revised Schedule of Activities Following Collection of Data for Primary Study Objective

After the collection of data for the primary study objective and most of the secondary objectives has been completed, patients who are still clinically benefiting from study treatment as judged by the investigator may be candidates for continuation of study treatment. Discussion with sponsor is required.

The following protocol sections should be disregarded: [Schedule of Activities](#) the original protocol and the trial procedures in [Section 6.2](#) Study Period, [7.2](#) Pharmacokinetics Assessments, [7.2.1](#) Blood Sample Collection for Pharmacokinetic Analysis, [7.2.2](#) Collection of Axitinib PK Samples, [7.2.3](#) Processing, Storage and Shipment of Axitinib PK Samples, [7.2.4](#) Collection and Processing of MK-3475 PK Samples, [7.2.5](#) Collection and processing of anti-MK3475 Antibody Samples, and [7.3](#) Translational and Pharmacodynamic Assessments. The investigator may schedule visits (unplanned visits) in addition to those listed in the [Schedule of Activities](#) table in order to conduct evaluations or assessments required to protect the well-being of the patient.

The following schedule of activities will be implemented for patients still on active treatment and long-term survival follow-up. Patients on axitinib monotherapy have the opportunity to continue axitinib treatment on a Pfizer-sponsored patient access program at the time of the discontinuation of survival status follow-up.

Protocol Activities and Forms to be Completed	Study Treatment 	Post-Treatment		
	Cycles ≥24 Day 1 -3/+3	End of Tx or Withdrawal  -3/+3	28 Days Post-Treatment -7/+7	Survival Follow-Up -7/+7
Physical Examination 	X	X		
In Clinic Blood Pressure, Pulse Rate 	X	X		
Home Blood Pressure Monitoring 	X	X		
Hematology 	Local Standard of Care	X		
Blood Chemistry 	Local Standard of Care	X		
Coagulation 	Local Standard of Care			
Urinalysis 	X			
12-lead ECG 	X	X		
Thyroid Function Tests 	X	X		
Pregnancy Test 	X	X		
Tumor Assessments 	Local Standard of Care and at End of Treatment			
Adverse Events 	X	X	X	
Concomitant Medications/Treatments 	X	X	X	
Study Treatment 	X			
Post Study Survival Status 			X	X

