7.4. Pharmacodynamic Biomarkers

For analysis of pharmacodynamic biomarkers, no values will be imputed for missing data.

Duplicate biomarker (i.e., more than one set of data for a particular visit) is not expected. For continuous data, if duplicate data is received, the results will be averaged and the average value will be used. The average value will be added to the analysis dataset. For non-continuous data, the results will be reviewed by the study team and a representative sample will be selected. The representative sample will be flagged in the analysis dataset.

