8.3.5. Analysis of Biomarker Endpoints

Translational and pharmacodynamic biomarkers will be summarized using the appropriate biomarker analysis set. Summaries of baseline and ratio to baseline values at post-treatment visits will be provided using N, mean, standard deviation, median, % CV (as appropriate) and minimum/maximum for circulating biomarkers serum and tumor RNA measurements for potential gene signature development. Summary statistics will be provided for baseline values of circulating markers including VEGF-A, VEGFR2, IL8 and T-cell receptors, and archival tumor and baseline *de novo* biospecimens markers such as PD-L1 for all biomarker evaluable patients. Post-baseline values will be summarized for biomarker evaluable patients in the dose expansion cohort, when available.

Correlations of biomarker results with measures of anti-tumor efficacy will be examined for dose escalation and expansion cohorts separately. Summary of level of biomarkers at baseline and/or ratio of values to baseline versus ORR category will be made by timepoint. Summary of PFS and DR will be provided for dose expansion cohort after stratification by a preset cutpoint of biomarker values at baseline and/or ratio of values to baseline by timepoint. Receiver Operating Characteristics (ROC) analysis may be conducted for significant test results ($p < 0.05$) in correlations of PFS and/or ORR with PD-L1 expression level. Receiver Operating Characteristics (ROC) analysis may also be performed if significant test results ($p < 0.05$) in correlations of ORR and/or PFS with tumor RNA measurements are observed.

Graphical display will be provided for level of biomarkers at baseline and/or ratio of values

to baseline at each timepoint. Box and Whisker plots will be produced for level of biomarkers at baseline and/or ratio of values to baseline versus ORR category by timepoint in dose escalation and expansion cohorts separately. Kaplan-Meier plots will be produced for PFS and DR after stratification by $<$ or \geq median levels of biomarkers at baseline and/or ratio of values to baseline at each timepoint in the dose expansion cohort.

All biomarker data will be listed.

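### Splitting PFS and DR by biomarker ratio at every timepoint takes in the End of Treatment blood sample, which only patients who have stopped treatment can have

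*SAP*

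**What the plan says.** SAP 8.3.5 sets out two outcome analyses stratified by biomarker, both in the expansion cohort:

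- Cutpoint summaries: "Summary of PFS and DR will be provided for dose expansion cohort after stratification by a preset cutpoint of biomarker values at baseline". The same sentence extends this to the ratio to baseline, by timepoint.
- Kaplan-Meier plots of PFS and DR, split below versus at or above "median levels of biomarkers at baseline and/or ratio of values to baseline at each timepoint in the dose expansion cohort".

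The section does not list the timepoints, set a landmark or use a time-dependent method. SAP 7.4 adds: "For analysis of pharmacodynamic biomarkers, no values will be imputed for missing data".

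The timepoints come from the protocol's Schedule of Activities. Footnote 24 says of serum: "Blood biospecimens will be collected at screening, Cycle 2 Day 1 predose, and End of Treatment/Withdrawal whichever comes first". Footnote 25 gives the same times for whole blood, and the table marks Cycle 2 and End of Treatment/Withdrawal as the only post-baseline draws. Protocol 7.3 gives the last sample a purpose: "Samples collected at the End of Treatment visit will also help understand potential mechanisms of resistance to the drug combination".

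**The concern.** PFS runs from Cycle 1 Day 1 and DR from first response (SAP 6.1). An End of Treatment ratio is known only when treatment ends, and confirmed progression is a main reason for ending it (Protocol 6.4). Two problems follow.

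First, patients still on treatment at the cutoff have no value and drop out of the plot. They tend to be the ones doing best, so both curves describe a subset selected on outcome.

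Second, patients are assigned to groups using a measurement often made on or after the event being plotted. A marker that rises with progression, or drifts with time on treatment, could separate the curves without predicting anything.

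Protocol 9.5.1.5 seeks the biomarkers most concordant with clinical outcome, and SAP 2.1 links this work to a future patient selection strategy. The risk is carrying the wrong candidate forward. The main PFS, DR and ORR estimates, the DLT endpoint and the ROC triggers (PD-L1 and tumor RNA, which have no End of Treatment tissue sample) are not affected.

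**Working it through.** The plan gives no figure on this point to reproduce. The check matches the SAP wording to the sampling schedule, then sizes the selection.

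**1. What the timepoints are.** For a blood ratio there are two: Cycle 2 Day 1 and End of Treatment/Withdrawal. No section of either document removes the second from the PFS and DR splits.

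**2. Who has the value.** Only patients who have stopped treatment by the cutoff, about 18 months after last enrolment (SAP 3). Stopping and progression need not coincide. Protocol 3.1 says "If radiologic imaging shows PD, tumor assessment should be repeated" to confirm it, and a patient still benefiting after confirmed progression may carry on: "he/she will be eligible for continued treatment with single agent axitinib, MK-3475 or axitinib combined with MK-3475". Toxicity stops come before progression. All three are varied below.

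**3. Whether waiting cures it.** Not fully. Appendix 6 tells sites to disregard Protocol 7.3, and its End of Tx column has no biomarker draw: "The following schedule of activities will be implemented for patients still on active treatment and long-term survival follow-up". It covers Cycle 24 onward, that is 23 x 21 = 483 days, or 15.9 months without delays. Patients who stop under it never get a value. The simulation does not model this.

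**4. Closed form.** Take exponential PFS with median m, treatment stopping at the event, and exactly 18 months of follow-up. With S(t) = 0.5^(t/m), the share sampled is 1 - S(18), and 12-month PFS among those sampled is [S(12) - S(18)] / [1 - S(18)].

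- m = 10.1 (axitinib alone, Protocol 1.2.2.2): S(12) = 0.439, S(18) = 0.291. Share 0.709; (0.439 - 0.291)/0.709 = 0.21, against 0.44 in all.
- m = 15 (assumed): S(12) = 0.574, S(18) = 0.435. Share 0.565; 0.25 against 0.57.
- m = 20 (assumed): S(12) = 0.660, S(18) = 0.536. Share 0.464; 0.27 against 0.66.

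**5. Simulation with the trial's features.** 400,000 patients per setting. From the documents: scans at week 12 then every 6 weeks, and the 18-month cutoff. Assumed: 12-month uniform accrual; 10% of events are deaths, with no sample if death ends treatment; toxicity stops at 0 or 1.5% per month, with PFS follow-up continuing; and the durations of treatment beyond progression. Each range runs from no toxicity stops to 1.5% per month.

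| Median PFS (months) | Treatment beyond progression | Share sampled | 12-month PFS, sampled | 12-month PFS, all |
|---|---|---|---|---|
| 10.1 | none | 71-78% | 33-38% | 47% |
| 10.1 | 4 weeks + median 3 months | 62-72% | 25-34% | 47% |
| 10.1 | 4 weeks + median 6 months | 51-64% | 22-33% | 47% |
| 15 | none | 59-70% | 39-48% | 60% |
| 20 | none | 50-64% | 42-55% | 68% |
| 20 | 4 weeks + median 3 months | 41-58% | 33-51% | 68% |

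The gap is smaller than in step 4, partly because earlier enrollees have up to 30 months of follow-up. Without toxicity stops every sample falls on or after the PFS event; with them, 59-79% do.

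**6. DR.** The documents give no DR figure, so medians of 12, 18 and 24 months are assumed, with first response at week 12, 18 or 24 in 70%, 20% and 10% of responders, and no treatment beyond progression.

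| Median DR (months) | Share sampled | 12-month DR, sampled | 12-month DR, all responders |
|---|---|---|---|
| 12 | 59-71% | 33-43% | 55% |
| 18 | 46-62% | 38-52% | 68% |
| 24 | 38-56% | 40-59% | 74% |

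These move by up to about 4 percentage points with how a minimum 4-week response is coded.

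**7. False separation.** This depends on how strongly the ratio is tied to time on treatment, which the documents do not give. With no link, a median split in the sampled subset behaves close to nominally. No rate is claimed.

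**The case against.** The strongest reply is that this reads generic wording too literally. SAP 8.3.5 never names End of Treatment, its and/or makes a ratio split optional, and Protocol 7.3 assigns that sample to resistance work. All true. It shows that the split is permitted, not that it is certain to be made. But with End of Treatment removed, a blood ratio at each timepoint means a single visit, and nothing in the documents removes it.

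Second, footnotes 24 and 25 end with a first-to-occur clause. If End of Treatment merely replaces Cycle 2 Day 1 in early stoppers, only about 0-1% of patients would have such a value and no median split would be possible. The table and Protocol 7.3 fit the other reading better, and the figures above assume it. On either reading the value exists only in stoppers.

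Third, the plots compare two halves of the same subset, so selection lowers both curves, and the subset-versus-all gap does not measure false separation. That stands: the figures size the selection, and the understatement applies only to these curves.

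Fourth, the work is exploratory. The SAP puts estimation ahead of testing, specifies no log-rank test for blood-marker splits, already plans descriptive ratio summaries, and leaves validation to later trials. That limits the weight of the point but does not make the split interpretable.

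**Conclusion.** The concern holds, as a minor point. Followed as written, SAP 8.3.5 groups patients by a blood value that exists only because treatment has ended. Under the assumptions above, without treatment beyond progression, the affected plots would omit about 22-50% of patients. They would show 12-month PFS about 9-14 points below the cohort at a 10.1-month median (47% minus 38% and 33%) and 13-26 points below at 20 months (68% minus 55% and 42%). The PFS gap widens with longer treatment beyond progression and with better efficacy; DR shows the same pattern. The direction needs no marker assumption, but the size rests on the assumed medians, accrual, toxicity rate and continuation times. Cycle 2 Day 1 and week-12 ratios do not share this defect.

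**What to change.** In SAP 8.3.5, name the timepoints for the PFS and DR stratification, covering both the cutpoint summaries and the Kaplan-Meier plots: baseline values, the Cycle 2 Day 1 ratio for blood, and the week-12 ratio for tumor. State that End of Treatment ratios are excluded from these splits and are summarized descriptively by reason for stopping treatment, which keeps the resistance use in Protocol 7.3. Landmark curves for the on-treatment ratios are optional.

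The cost is one sentence and minor programming, with no new data. The End of Treatment Kaplan-Meier plots are lost, but they could not have been interpreted.

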8.4. Summary of Secondary Efficacy Analyses

Endpoint	Analysis Population	Statistical Method	Missing Data	Analysis Type/Timing
ORR	Response Evaluable	Exact method based on F-distribution (95% CI) (See 8.3.2)	See Section 6.1	Secondary analysis
DR	Subgroup of pts with OR from the Response Evaluable	K-M method (median and 95% CI) (See 8.3.2)	See Section 6.1	Secondary analysis
TTR	Response Evaluable	Univariate (median and 95% CI) (See 8.3.2)	See Section 6.1	Secondary analysis
PFS	Response Evaluable	K-M method (median, 6 and 12m-PFS and 95% CIs) (See 8.3.2)	Censor patients on the day of the last evaluable tumor assessment documenting absence of disease progression for ... (See Section 6.1)	Secondary analysis
OS	Response Evaluable	K-M method (median and 95% CIs) (See 8.3.2)	See Section 6.1	Secondary analysis

CI: Confidence intervals; DR: Duration of Response; K-M: Kaplan-Meier; OR: Objective Response; ORR: Objective Response Rate; PFS: Progression-free Survival; TTR: Time to Response; OS: Overall Survival

10. APPENDICES

Appendix 1. Programming Specifications for AE Analyses

a. Time to AE onset

1. Definition

Time to AE onset (days) will be calculated as $AE\ start\ date - first\ dose\ date + 1$. The definition and calculations are similar for time to Grade 3/4 AE onset.

AE start date

The Date of Onset for the first occurrence of the AE based on the Log AE CRF page.

First dose date

For AE summaries of the lead-in PK period: The date of the first dose taken from the Axitinib Dosing CRF page.

For AE summaries of the treatment period starting at C1D1: The date of the first dose taken from the MK-3475 Dosing CRF page.

For AE summaries of the entire treatment period (including by cycle): The date of the first dose taken from either the Axitinib or MK-3475 Dosing CRF page, whichever occurs first.

b. Duration of AE

1. Definition

Duration of AE (days) is defined as the cumulative duration across episodes of the specific AE (by preferred terms) where duration for each episode is calculated as $AE\ end\ date - AE\ start\ date + 1$ excluding any overlap. Duration of AE is defined for subjects with the AE.

AE start date

The Date of Onset based on the Log AE CRF page.

AE end date

The Date Resolved based on the Log AE CRF page.

2. Censoring

AE resolution is considered an event (censoring variable=1). If a subject has an AE that was ongoing (does not have to be the last AE) at the time of analysis, the time is censored (censoring variable=0) at the last available on treatment visit date. Subjects who die prior to resolution of the AE will be censored at the *date of death*. If the date of death is the same as the date of the resolution of the AE, the subject will be censored at that date (i.e. resolution will not be considered an event) and only if the AE is the AE that resulted in death will it be counted as an event.

Date of death

[figure not shown]
Death date is based on the Notice of Death CRF page.

3. Clustered Events

[figure not shown]
For clustered events, a patient could have multiple events in the cluster which may overlap. In this case, AE duration will be summed across all events in the cluster accounting for the overlap (i.e. overlapping periods between events in the same cluster are not double-counted). Lags between events in the same cluster are not included in the duration.

The following scenarios provide examples of the calculation for 2 events in the same cluster. The extension to 3 or more events of the same cluster is similar.

[figure not shown]
- **TWO EVENTS OF THE SAME CLUSTER WHERE ONE EVENT COMPLETELY CONTAINS THE OTHER EVENT**

- **CERTAIN PORTIONS OF TWO EVENTS IN THE SAME CLUSTER OVERLAP**

[figure not shown]

- **TWO EVENTS OF THE SAME CLUSTER ARE CONTIGUOUS TO EACH OTHER**

$$duration = enddate2 - startdate1 + 1$$

- **TWO EVENTS OF THE SAME CLUSTER ARE NON-OVERLAPPING**

$$duration = (enddate1 - startdate1 + 1) + (enddate2 - startdate2 + 1)$$

c. AE Prevalence

1. Definition

AE prevalence is defined as the number of patients with an AE in a particular time period (including both new cases with an onset date during the specified time period AND cases with an AE continued from a previous time period) divided by the number of patients at risk during the specified time period. The number of patients at risk includes all subjects except those who either have discontinued or died prior to the specified time period.

AE prevalence will be presented for the entire study period, separately for the lead-in PK period and by cycle (Cycle 1, Cycle 2 and Cycles beyond 2), as well as for the entire treatment period starting at C1D1.

2. Assumptions

For AE summaries of the study period starting at C1D1 the following apply:

- A patient is counted in the numerator if the patient has an onset date of the AE during Cycle 1 OR for patients with a 7 day lead-in PK period there is an increase in grade of the AE after the first dose of MK-3475 (C1D1) or if there is a decrease and then subsequent increase during treatment with the combination.
- The denominator will include subjects who have received at least one dose of MK-3475.

For AE summaries of the entire study period including by cycle (Lead-in PK period, Cycle 1, Cycle 2 and Cycles beyond 2) the following apply:

- Patients are counted for an AE in each cycle up until the cycle where the AE resolved. Thus, the calculation conservatively assumes that if the AE resolved in a cycle, it resolved at the end of the cycle.
- For Lead-in PK period, a patient is counted in the numerator if the patient has an onset date of the AE during the Lead-in period.
- For Cycle 1, a patient is counted in the numerator if the patient has an onset date of the AE during Cycle 1 OR an onset date during the Lead-in PK phase that is still ongoing in Cycle 1 (did not have a resolution date in the Lead-in phase).
- For Cycle 2, a patient is counted in the numerator if the patient has an onset date of the AE during Cycle 2 OR an onset date during the Lead-in PK phase or Cycle 1 that is still ongoing in Cycle 2 (did not have a resolution date in the Lead-in phase or Cycle 1).

- For Cycles ≥ 2 , a patient is counted in the numerator if the patient has an onset date in Cycles ≥ 2 OR an onset date in a previous cycle that is still ongoing (did not have a resolution date in Cycle 1 or earlier).
- The denominator for a particular time period will include subjects who are at risk prior to the time period. The number at risk includes all subjects except those who either have discontinued (based on the 'Subject Summary' CRF) or died prior to the specified time period (i.e. Death Date based on 'Notice of Death' CRF is prior to start of time period).

